11.1.2 Statistical analysis for the secondary endpoints

For the secondary analysis of a) all-cause mortality at 48 hours and day 7, 60, 180, b) the composite endpoint of death, cardiac transplant, escalation to LVAD, stroke at days 30, 60, 180 the same analysis strategy will be performed as for the primary endpoint.

Unpaired t-test will be performed, after checking for normality of the variable's distribution, for the outcomes mentioned below. Importantly, In case of non-normal distributions (which is highly likely for all duration data), non-parametric tests will be performed.

- VA-ECMO duration
- cumulated amount of administered fluids and duration of vasopressors use
- duration to normalization of lactate
- Number of days alive without organ failure(s), defined with the SOFA score and its components (respiratory, liver, coagulation and renal), between inclusion, D7 and D30
- duration of mechanical ventilation and the number of days, between inclusion and day 30/ day 60/ day 180, alive without a mechanical ventilation
- number of days alive without renal replacement therapy, and the number of days, between inclusion and day 30/ day 60/ day 180, without renal replacement therapy
- duration of ICU stay, of hospitalization
- number of severe and moderate bleeding complications (gusto-definition) and number of packed red blood cells transfused under VA-ECMO

Chi-square tests (or Fisher exact test in case of insufficient number of expected patients in on of the 2x2 cell) will be performed for the outcomes mentioned below:

- Pulmonary, blood and VA-ECMO cannulaes infections

To illustrate the association, an odd-ratio will be provided.

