MAIN OBJECTIVE	The study objective is to determine whether early moderate hypothermia $(33^{\circ}C \le T^{\circ}C \le 34^{\circ}C)$ is superior to normothermia $(36^{\circ}C \le T^{\circ}C \le 37^{\circ}C)$ in patients with cardiogenic shock treated with VA-ECMO with respect to 30-day mortality.
SECONDARY OBJECTIVES	Evaluation of the impact of moderate hypothermia on:
OLCONDART OBJECTIVES	 Mortality during hospitalization and up to 180 days. VA-ECMO weaning time Adverse cardiovascular events Necessity of fluid and vasopressor (norepinephrine, epinephrine) Lactate clearance
	- Duration of organ failure

	 The risk of bleeding The risk of Sepsis (pulmonary, blood, venous lines, VA-ECMO) 						
	cannulaes) All-cause mortality at day 30 following randomization (i.e. 30 day mortality)						
SECONDARY ENDPOINTS	 All-cause mortality at 48 hours and day 7, 60, 180 VA-ECMO duration Composite endpoint of death, cardiac transplant, escalation to LVAD, stroke at days 30, 60, 180 Cumulated amount of administered fluids and duration of vasopressors use in ICU Duration to normalization of lactate Number of days alive without organ failure(s), defined with the SOFA score and its components (respiratory, liver, coagulation and renal), between inclusion, D7 and D30. Duration of mechanical ventilation and the number of days between inclusion and day 30, day 60 and D180, alive without mechanical ventilation Number of days, between inclusion and day 30, day 60 and D180, without renal replacement therapy Duration of ICU stay, of hospitalization Number of severe and moderate bleeding complications (GUSTO-definition, N Engl J Med. 1993;329:673–682) and the number of packed red blood cells transfused under VA-ECMO Infection probability: pulmonary, blood and VA-ECMO cannulaes 						
STUDY DESIGN	A multicenter, prospective, controlled, randomized (moderate hypothermia						
	$33^{\circ}C \le T^{\circ}C \le 34^{\circ}C$) during 24 hours \pm 1h versus normothermia $36^{\circ}C \le T^{\circ}C \le 37^{\circ}C$, comparative open trial will be conducted on two parallel groups of patients with cardiogenic shock treated with VA-ECMO.						
STUDY	Venoarterial ECMO (VA-ECMO) will be implanted in accordance to the local						
TREATMENTS/STRATEGIES PROCEDURES	exception of temperature control, all other diagnostic and therapeutic procedures will be done according to the current standard of care at the tertiary cardiovascular center.						

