3.3 STUDY OUCOME MEASURES

3.3.1 **Primary endpoints**

All-cause mortality at day 30 following randomization (i.e. 30 day mortality)

3.3.2 **Secondary endpoints:**

[figure not shown]
- All-cause mortality at 48 hours and day 7, 60, 180
- VA-ECMO duration
- Composite endpoint of death, cardiac transplant, escalation to LVAD, stroke at days 30, 60, 180
- Cumulated amount of administered fluids and duration of vasopressors use in ICU
- Duration to normalization of lactate
- Number of days alive without organ failure(s), defined with the SOFA score and its components (respiratory, liver, coagulation and renal), between inclusion, D7 and D30
- Duration of mechanical ventilation and the number of days between inclusion and day 30/ day 60/ day 180, alive without mechanical ventilation
- Number of days alive without renal replacement therapy, and the number of days, between inclusion and day 30, day 60 and day 180, without renal replacement therapy

- Duration of ICU stay, of hospitalization
- Number of severe and moderate bleeding complications (GUSTO-definition, N Engl J Med. 1993;329:673–682) and the number of packed red blood cells transfused under VA-ECMO
- Infection probability: pulmonary, blood and VA-ECMO cannulaes

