11.2 SAMPLE SIZE CONSIDERATION

We considered that mortality in cardiogenic patients supported with VA-ECMO will be 50% (based both on ELSO data, [name] data (*Crit Care Med.* 2008 May;36(5):1404-11) and study principal investigator's personal data (database of 150 patients)

The objective of the study is to demonstrate the superiority of the treatment with VA-ECMO plus moderate hypothermia as compared to VA-ECMO alone on mortality.

Therefore, considering a total event risk (for the primary endpoint) of 50 % in the control group, a sample size of N = 167 patients/group will detecting a 15% absolute difference in favor the VA-ECMO group using a chi-square test with a 80 % power and considering a two-sided global alpha level of 5% using the LanDe Mets method with O'BrienFleming boundary for one interim analysis (efficacy and futility) after inclusion of 2/3 of the patients.

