11.3 DEGREES OF STATISTICAL SIGNIFICANCE

A bilateral p value lower than 4.9% will be considered significant for the final analysis. A p value threshold lower than 5% is mandatory given the planned interim analyses to ensure a global alpha level at 5%.

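### Raw durations of VA-ECMO, vasopressors, ventilation and stay are compared between arms with no handling of death, at a planned day-30 mortality of 50% v 35%

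*Protocol*

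**What the plan says.** Protocol section 11.1.2 lists the continuous secondary outcomes and assigns them an unpaired t-test after a normality check. It then states: "In case of non-normal distributions (which is highly likely for all duration data), non-parametric tests will be performed". The list includes VA-ECMO duration, vasopressor duration, time to lactate normalisation, duration of mechanical ventilation, and ICU and hospital stay.

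Section 11.8 puts every randomised patient in the analysis. Section 11.6 deals with missing data for the primary outcome only. Section 11.2 sets the mortality level by "considering a total event risk (for the primary endpoint) of 50 % in the control group" and aims at "detecting a 15% absolute difference", with "a sample size of N = 167 patients/group".

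Some outcomes carry a survival condition. Sections 3.3.2 and 11.1.2 count days alive without organ failure and days alive without mechanical ventilation. For renal replacement they list a count of days alive without it and then a second count: "and the number of days, between inclusion and day 30, day 60 and day 180, without renal replacement therapy". The synopsis has only this: "Number of days, between inclusion and day 30, day 60 and D180, without renal replacement therapy".

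**The concern.** A duration of support has no clear meaning for a patient who dies on support, and here a large share of patients are expected to die. A two-sample test on the raw duration needs one number per patient, and both obvious choices cause trouble:

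- **The duration ends at death.** A patient who dies on day 1 then has among the shortest ECMO, vasopressor, ventilator and ICU times, on a scale where shorter is normally read as better.
- **Decedents are left out.** The comparison is then between survivors of each arm, a group that treatment itself is expected to change. It also departs from section 11.8.

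Lactate is a separate problem. A patient who dies before normalisation has no value to enter.

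At stake is the reading of several secondary endpoints. A mortality difference could create a difference in duration, or hide one, when recovery on support is the same in both arms.

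**Working it through.** **Step 1: planned deaths.** Inputs from section 11.2 are 50% v 35%, 80% power and two-sided 5%. The unpooled formula gives n = (1.96 + 0.842)² × (0.50×0.50 + 0.35×0.65) / 0.15² = 7.849 × 0.4775 / 0.0225 = 166.6. This reproduces the stated 167 per group (the pooled version gives 170). Deaths by day 30 are 167×0.50 + 167×0.35 = 83.5 + 58.45, about 142 of 334, or 42.5%.

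**Step 2: effect on a raw duration that ends at death.** The protocol gives no event times, so these are assumptions:

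- Time to liberation from support is lognormal with log-SD 0.7 and median 7 or 14 days, the same in both arms.
- Death times among those who die by day 30 are exponential with median 3, 5 or 8 days, capped at day 30.
- Duration = min(liberation, death), with 167 per arm.
- Mann-Whitney test at 0.049, the level in section 11.3 ("A bilateral p value lower than 4.9% will be considered significant for the final analysis"), with 500 trials per row.

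Mortality is 50% in controls and 35% under hypothermia:

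| Median liberation (d) | Median death (d) | Median duration, control | Median duration, hypothermia | Rank test significant |
|---|---|---|---|---|
| 7 | 3 | 4.5 | 5.3 | 35% |
| 7 | 5 | 5.2 | 5.7 | 24% |
| 7 | 8 | 5.7 | 6.0 | 13% |
| 14 | 3 | 7.0 | 9.2 | 52% |
| 14 | 5 | 8.5 | 10.2 | 39% |
| 14 | 8 | 9.7 | 11.0 | 28% |

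Death cuts the duration short in 24–45% of controls and 17–32% of hypothermia patients. The t-test is significant in 12–35% of the same trials. With the mortalities swapped, hypothermia shows the shorter duration and the rank test is significant in 12–55%. With equal 50% mortality and equal death timing, rejection is 2–7%, around the nominal level. With equal mortality but earlier deaths under hypothermia (median 2 v 5 days, liberation 7 days), medians are 3.9 v 5.2 days and about 77% of trials are significant. The distortion therefore comes from differential death.

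**Step 3: does the direction hold?** Not always. The table lets decedents share the survivors' liberation process, so they can only have shorter durations. Suppose instead that decedents stay on support until death (median 8 days) while survivors are liberated at a median of 5 days. At 50% v 35%, medians are then 6.1 days (control) v 5.7 (hypothermia). About 9% of trials are significant, and some 94% of those show a shorter duration with hypothermia. With both medians at 5 days, rejection is about 5%. The direction depends on whether decedents spend less or more time on support than survivors.

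**Step 4: a score that accounts for death.** On the Step 2 patients, support-free days to day 30, scored zero for a death, average 13.8 (hypothermia) v 10.6 (control) with liberation at 7 days, and 9.2 v 7.1 at 14 days. With mortality swapped, the advantage moves to control by about the same amount.

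**Step 5: the renal count without the alive condition.** Assume 45% of patients receive renal replacement for a median of 7 days, with deaths at a median of 5 days and mortality 50% v 35%. If days after death are counted as free, the 30-day means are 26.9 (control) v 26.6 (hypothermia). Counting only days alive and free, they are 15.5 v 18.6.

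**The case against.** The protocol nowhere says that a duration stops at death or that decedents are excluded. Such derivation rules are commonly left to the statistical analysis plan, which is not at hand. No rank test is named either: the term non-parametric does not exclude a log-rank test, Gray's test or a worst-rank score. These are secondary endpoints, mortality is tested at several time points beside them, and three of the outcomes already have an alive-and-free count.

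Much of this stands, and it rules out stronger readings that a reader might infer:

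- **That the plan states that death scores as a good outcome.** It does not. That is the result of one reading, and the other reading fails differently.
- **That a life-saving effect would generally look like harm.** Step 3 shows that the direction depends on times the documents do not give.
- **That early death scores as better for lactate.** The value is undefined, not favourable.
- **That renal replacement has no survival-conditioned count.** Sections 3.3.2 and 11.1.2 do list one. Only the synopsis lacks it, and treating days after death as free is one reading of the unqualified count.
- **That about half of all patients die.** That is the control-arm assumption; the design average is 42.5%.

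The objection does not remove the point. As the fallback from an unpaired t-test, a non-parametric test is naturally read as a rank test on the same raw durations. A derivation rule alone does not repair that comparison: truncating at death and dropping decedents both fail. A competing-event test or a worst-rank score would repair it, but that replaces the comparison or redefines the outcome, and section 11.1.2 calls for neither.

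**Conclusion.** The concern holds as a weakness in how section 11.1.2 fixes the secondary analyses. For VA-ECMO, vasopressors, ICU stay and hospital stay, raw duration is compared with no treatment of death and no alive-and-free companion. Time to lactate normalisation also has no companion, and no defined value for those who die first. Ventilation has a companion count, but its raw duration is still compared.

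With identical recovery in both arms and the planned 50% v 35% mortality, the rank test is significant in roughly 5% to 50% of simulated trials. That range rests wholly on assumed event times. What does not rest on them is that a mortality difference can enter the duration comparison, and that the plan has nothing to separate the two. The renal wording is a smaller matter: the synopsis disagrees with the body, and the second count in the body is ambiguous about death. The primary mortality test and the 167 per group are unaffected. The change should be made, but the trial's main conclusion does not depend on it.

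**What to change.** 1. In section 11.1.2, base the between-arm comparison for VA-ECMO weaning, vasopressor stop, extubation, ICU and hospital discharge, and lactate normalisation on a method that accounts for death. Either use time to event with death as a competing event (cumulative incidence with Gray's test, or cause-specific hazards), or use days alive and free to day 30 with death giving no further free days. The second is a composite that also moves with mortality, so report it beside the mortality result.
2. Report raw durations descriptively, by arm and survival status, without a test.
3. Align the synopsis renal endpoint with the alive version in sections 3.3.2 and 11.1.2. Drop the second renal count there, or add the alive condition to it.

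The cost is wording plus modest programming. Date of death is already collected under section 4.1.9, and start and stop dates are needed for the durations in any case.

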3.2 SECONDARY OBJECTIVES

Evaluation of the impact of moderate hypothermia on:

- Mortality during hospitalization and up to 180 days
- VA-ECMO weaning time
- Adverse cardiovascular events
- Necessity of fluid and vasopressor (norepinephrine, epinephrine)
- Lactate clearance
- Duration of organ failure
- Mechanical ventilation support use
- Renal replacement therapy use
- Duration of ICU stay and total duration of hospitalization
- The risk of bleeding
- The risk of Sepsis (pulmonary, blood, venous lines, VA-ECMO cannulaes)

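### Raw VA-ECMO, vasopressor, ICU and hospital durations are tested although death also ends each of them, so the result mixes the mortality effect with any effect on duration and can point either way

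*Protocol*

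**What the plan says.** Protocol 3.3.2 lists "VA-ECMO duration", the duration of vasopressor use in ICU, and the durations of ICU and hospital stay as secondary endpoints, defined only as lengths. Section 11.1.2 assigns them an unpaired t-test after a normality check, with this fallback: "In case of non-normal distributions (which is highly likely for all duration data), non-parametric tests will be performed". The stays appear in that list as "duration of ICU stay, of hospitalization".

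The matching objective in 3.2 is "VA-ECMO weaning time", which is a time to a favourable event and not a run length.

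For ventilation the plan does add a measure that takes account of death: "Duration of mechanical ventilation and the number of days between inclusion and day 30/ day 60/ day 180, alive without mechanical ventilation". Organ failure and renal replacement also have counts of days alive without the condition. VA-ECMO, vasopressors, ICU stay and hospital stay have none.

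Section 11.8 includes every randomized patient. Section 11.6 deals only with missing 30-day vital status. Section 11.2 sets the planning scenario: "considering a total event risk (for the primary endpoint) of 50 % in the control group" and a "15% absolute difference in favor the VA-ECMO group using a chi-square test with a 80 % power".

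**The concern.** Each of the four clocks stops either at a good event (weaning, end of vasopressors, discharge) or at death. A two-sample test on the length cannot tell the two apart. Choosing between a t-test and a rank test deals with skewness, not with this.

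If hypothermia lowers mortality as planned, the arms differ in how many durations death cuts short. A trial that succeeds on its primary endpoint could then report longer VA-ECMO, ICU or hospital stay only because patients survived. With late deaths it could report a shortening that is equally spurious. The synopsis (potential impact) and section 1.4.1 present shorter ICU and hospital stays as a possible benefit with lower cost, so these results bear on a claim that the protocol itself makes.

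**Working it through.** **Planning scenario.** Inputs from 11.2: control mortality 50%, a 15-point reduction (so 35%), 80% power, "two-sided global alpha level of 5" per cent. The unpooled formula gives n = (1.960 + 0.842)² × (0.50×0.50 + 0.35×0.65) / 0.15² = 166.6, so 167 per group, as stated. Expected deaths are 167 × 0.50 = 83.5 and 167 × 0.35 = 58.5, about 84 versus 58.

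**Inputs that the documents do not give.** There is no duration of support or stay and no timing of deaths. All durations below are assumptions. Each check sets the true effect on duration to zero.

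**Check 1: fate first, then duration.** Each patient dies with probability 0.50 or 0.35. Durations are log-normal with the same distribution in both arms, separately for survivors and for deaths (times to death capped at day 30). There are 167 per arm, 1,500 trials per row, and a two-sided rank-sum test at 5%. The log-scale SD is 0.5-0.6 in survivors and 0.9 in deaths (0.5 in the 7/7 and 7/10 rows). The last column applies the same test to days alive and free to day 30, with 0 for death.

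| Outcome (median days, survivors / deaths) | Raw: hypothermia falsely longer | Raw: falsely shorter | Alive-and-free days: better |
|---|---|---|---|
| ICU 18/5 | 47% | 0% | 54% |
| ICU 14/7 | 20% | 0.1% | 63% |
| Hospital 30/6 | 56% | 0% | 32% |
| Hospital 30/10 | 41% | 0% | 31% |
| VA-ECMO 7/3 | 28% | 0% | 72% |
| VA-ECMO 7/5 | 10% | 0.7% | 69% |
| VA-ECMO 7/7 | 3% | 3% | 69% |
| VA-ECMO 7/10 | 0.3% | 17% | 72% |
| Vasopressor 4/3 | 7% | 0.5% | 70% |

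The nominal rate is 2.5% in each direction. In the ICU 18/5 row the median stay is 10.8 versus 13.3 days, and in the hospital 30/6 row 15.8 versus 21.0 days, with no true effect.

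**Check 2: timing of death.** With no weaning before day 2 and a median of 6 days in weaned patients, the rate of falsely longer VA-ECMO falls from 48% (median death at day 2) to 3% (day 6). It then reverses to 15% falsely shorter (day 10).

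**Check 3: competing constant hazards.** Let a fraction f die on VA-ECMO and let the weaning hazard be w = 0.15/day in both arms. The total exit hazard is w/(1−f).

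- Mean run: (1−f)/w = 0.50/0.15 = 3.3 days versus 0.65/0.15 = 4.3 days.
- Chance that a hypothermia run exceeds a control run: 0.65/(0.65 + 0.50) = 0.565. This does not depend on w, so varying w tests nothing for the raw durations.
- Rank-sum z: (0.565 − 0.5) × √(12 × 167² / 335) = 2.06. At the 4.9% threshold of 11.3 (critical value 1.97), the rate of falsely longer is Φ(2.06 − 1.97) = 54%; simulation gives 53-54%.
- With 40% versus 28% dying on VA-ECMO the rate is 30%, and with 30% versus 21% about 15%.
- Weaned patients only (83.5 versus 108.6): z = 0.0652 × √(12 × 83.5 × 108.6 / 193) = 1.55, so the rate is Φ(1.55 − 1.97) = 34%. Restricting to weaned patients is therefore not a safe repair.
- Days alive and off VA-ECMO to day 30 show benefit with identical weaning in about 43%, 25% and 14% of trials in the three settings.

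**The case against.** **Direction.** A reader might infer that a hypothermia arm with fewer deaths will look worse. The documents do not support that. It requires deaths to come earlier than weaning or discharge, and they give no timing. The 7/7 row shows no bias and the 7/10 row a bias in favour of hypothermia. Only *can look worse* is justified. The reversal does not rescue the test, because its result still depends on when patients die.

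**Size.** The 53-54% from constant hazards should not be taken as the headline for VA-ECMO. That model lets weaning start at hour 0, whereas Appendix A, item 5, says weaning should not be attempted in the first 48 hours. It would wean 1 − exp(−0.30 × 2) = 45% of the weaned control patients before then. This objection stands, and the size must be given as a range that includes zero and reversal.

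**Scope.** Ventilation, organ failure and renal replacement should not be added to the defect, because they already have counts of days alive without the condition. Mortality at several time points is also reported alongside, which helps a careful reader but does not correct the tests.

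**Legitimate use.** Total days including those of patients who die are a sensible measure of resource use. This stands as a reason to keep raw stay as description, not as a test of clinical benefit.

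**Left to the SAP.** An SAP that is not shown may add a rule for deaths, and 11.1.2 does not name the non-parametric test; rank-sum is the natural reading. But the protocol itself fixes the endpoint as a raw length, with a two-sample test, in all randomized patients. That is a choice made, not a detail left open.

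**The replacement also carries mortality.** This is true. Alive-and-free days show benefit in roughly 14-72% of trials with no true duration effect, so they cannot be read as a clean measure of duration.

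**Conclusion.** The point holds for four secondary outcomes: VA-ECMO duration, vasopressor duration, ICU stay and hospital stay. As written, their tests mix mortality with duration, and for VA-ECMO the endpoint does not match the objective of weaning time.

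With 167 per arm, 50% versus 35% mortality and no true duration effect, hypothermia is falsely longer in about 20-56% of trials for ICU and hospital stay. For VA-ECMO and vasopressors the figure runs from about 0% to about 50%, with reversal to falsely shorter in about 15-17% if deaths come well after weaning. These rates rest on assumed durations and death times. That the result depends on death timing is certain; its size and direction in this trial are not. The 30-day mortality comparison is unaffected.

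**What to change.** In 3.3.2, 11.1.2 and the synopsis:

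1. Make the tested endpoints days alive and free of VA-ECMO, of vasopressors, of ICU and of hospital to a fixed day (day 30, for example). Score 0 for patients who die before that day and compare by rank test.
2. For the weaning objective, analyse the cumulative incidence of successful weaning, with death (and transplant or assist device) as competing events.
3. Keep the raw durations as description by vital status, including total days for resource use.
4. State that alive-and-free days partly restate mortality and must be read beside the primary result and the competing-risk analysis.

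The cost is wording. The start, stop and death dates are already needed for the durations and vital status, and no extra patients or visits are required.

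### Time to normal lactate has no value for patients who die first, yet section 11.1.2 assigns tests that need one value per patient and gives no rule for these deaths

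*Protocol*

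**What the plan says.** Protocol section 3.2 names "Lactate clearance" as a secondary objective. The only endpoint in section 3.3.2 that serves it is "Duration to normalization of lactate".

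Section 11.1.2 places this endpoint, as "duration to normalization of lactate", in a list governed by one rule: "Unpaired t-test will be performed, after checking for normality" and then "In case of non-normal distributions (which is highly likely for all duration data), non-parametric tests will be performed". The same list holds fluid volumes and transfusion counts. It also holds outcomes that build death into their definition, for example "Number of days alive without organ failure(s), defined with the SOFA score and its components".

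Section 11.2 plans on mortality as follows: "considering a total event risk (for the primary endpoint) of 50 % in the control group", with a "15% absolute difference" to be detected. Section 11.8 puts all randomised patients in the analysis. Section 11.6 gives a missing-data rule for the primary outcome only. Kaplan-Meier curves and hazard ratios are planned for mortality (11.1.1) and, by reference, for the composite endpoint (11.1.2), but not for lactate. No section says what value a patient receives who dies before lactate normalises.

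**The concern.** Time to normal lactate is a time-to-event outcome, and death prevents the event. In this population early death is common, and it should differ by arm if hypothermia works. The ordinary ways to apply a t-test or rank test to durations are these:

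- **Use only patients who normalised.** The sickest patients, who would have cleared lactate slowly, drop out, and more of them drop out of the arm with more deaths. Those left in that arm look faster.
- **Enter the death time as the duration.** An early death then scores as quick clearance.

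Both handlings favour the arm with more early deaths. With lower mortality under hypothermia, the endpoint tilts towards slower clearance under hypothermia even when kinetics are the same. With higher mortality it tilts the other way, and a harmful treatment could appear to clear lactate faster. In either case the comparison is no longer one between the groups as randomised.

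**Working it through.** **Planning figures.** Section 11.2 gives 50% control mortality, a 15-point reduction (hence 35%), and 167 per group. The unpooled formula reproduces the sample size: (1.960 + 0.842)² × (0.50×0.50 + 0.35×0.65) / 0.15² = 7.849 × 0.4775 / 0.0225 = 166.6, so 167. The pooled formula gives 170. The sample size is not in dispute, and the protocol states no figure for lactate.

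**How many could lack a value.** If every 30-day death came before normalisation: 167 × 0.50 = 83.5 controls and 167 × 0.35 = 58.5 hypothermia patients, about 142 of 334. The true number is lower, and the protocol does not give it.

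**Model A (assumed).** There are 167 patients per arm and 1,500 trials per setting. Time to normal lactate is log-normal with median 24 or 48 h and log-SD 0.9. Deaths by day 30 are 50% v 35%. Time of death is log-normal with median 36 or 72 h and log-SD 1. Both processes are moderately correlated with severity (0.5 for the lactate time). A Wilcoxon test is run at two-sided 0.049, so about 2.5% in each direction. Results with identical kinetics:

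- Controls without a value: 12% to 32%.
- Patients with a value only: hypothermia declared slower in about 4% to 10% of trials.
- Death time entered as the duration: hypothermia declared slower in 4% to 9% in one set of runs and 4% to 19% in another.

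**Model B (assumed, different structure).** A shared severity term u ~ N(0,1) drives both hazards. The normalisation hazard is (1/1.5 per day) × exp(−u), and the death hazard is h₀ × exp(u). h₀ is set so that 10% to 40% of controls have no value by day 30. There are 3,000 trials per setting, with a Mann-Whitney test on patients with a value at two-sided 5%. Rejection rates:

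| Controls without a value | No effect on either | Death HR 0.6, no lactate effect | Lactate HR 1.5, death HR 0.6 | Lactate HR 1.5, death HR 1 | Lactate HR 1.5, death HR 1.5 |
|---|---|---|---|---|---|
| 10% | 4.9% | 6.5% | 44.1% | 55.6% | 67.1% |
| 20% | 5.0% | 8.6% | 29.1% | 48.8% | 66.6% |
| 30% | 5.3% | 12.0% | 20.1% | 43.6% | 63.2% |
| 40% | 4.8% | 13.5% | 12.0% | 33.8% | 60.0% |

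The test holds its level when treatment affects neither outcome. A mortality effect alone raises the rejection rate to between 6.5% and 13.5%. In the last three columns the effect on lactate is fixed and only the effect on death changes. The same lactate benefit is detected in 12% to 44% of trials when hypothermia saves lives and in 60% to 67% when it costs lives. That is the selection bias, in both directions.

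**The case against.** **The protocol does not prescribe a subset analysis.** Section 11.8 includes every randomised patient, and section 11.1.2 expects durations to be non-normal, so the t-test is not the likely route. A worst-rank, log-rank or Gray test would fit the words used. On this view only a scoring rule is missing, and the SAP could supply it. Part of this stands: restriction to normalisers is the natural execution of the text, not something the protocol states. But the t-test branch is fixed in the protocol and does not suit this endpoint. The same instruction covers volumes and counts, for which it plainly means an ordinary rank test. Neighbouring endpoints build death in and this one does not. Without a rule, section 11.8 cannot be met here.

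**A reader might infer that the listed test loses power.** Under the planned mortality with 25% faster normalisation, model A gives about 43% to 63% among patients with a value against 81% to 87% with death ranked worst. Most of that gap is the mortality effect entering the second test. With equal 50% mortality in both arms, the figures are about 65% to 74% and 56% to 78%, and worst-rank is lower in one setting. Power is therefore not the ground for the change.

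**The alternatives do not isolate kinetics either.** With identical kinetics and the planned mortality, the worst-rank test in model A favours hypothermia in about 4% to 16% of trials. This is true and must be stated. It remains a comparison of all patients as randomised, on an outcome that can be defined.

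**Weight.** This is one of many secondary endpoints. In the planned case the bias runs against hypothermia, so it does not create a false claim of benefit there. Death also cuts short the ECMO, vasopressor, ventilation and stay durations in the same list. Lactate differs because death leaves its duration undefined, not just shortened.

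**Conclusion.** The concern holds as a matter of selection bias. The assigned tests need a duration that patients who die early do not have, and the protocol gives no rule for them. Under the planned mortality and the assumptions of model A, the false finding of slower clearance with hypothermia is about 4% to 10% one-sided against 2.5%. The direction reverses if hypothermia raises mortality.

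These sizes rest on assumed lactate distributions, death timing and correlation with severity, none of which the protocol gives. The direction does not depend on the exact values: it appears in two differently built models. The primary endpoint, sample size and interim analysis are untouched. The change is worth making but does not threaten the trial's main conclusion.

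**What to change.** In section 11.1.2, take this endpoint out of the t-test list and analyse all randomised patients by one of two methods, chosen in advance:

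- cumulative incidence of first normal arterial lactate from randomisation to a fixed horizon (for example day 7), with death before normalisation as a competing event, compared by the Gray test; or
- a rank test in which death before normalisation, or never reaching normal, is ranked worst.

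State that the result combines clearance and early survival, and report the proportion already normal at inclusion.

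The cost is a few lines of text. Arterial lactate (section 4.1.4) and date of death (section 4.1.9) are already collected, and no clinical procedure changes. The price is interpretive: the endpoint no longer speaks to lactate kinetics alone, so it should be read beside the mortality results.
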